3.7 Endpoints/outcomes

Table 16 Endpoints/outcomes

The following table displays which measures are collected at each of the assessment points:

Work	Measure	Detail	Size	Base	4	3	12
Pckge				line	weeks	months	months
6/7	Pre-screening	Language	1 item	Х			
	(pre consent)	Country under which participating,	5 items				
		Gender, ethnicity, confirmation of likely eligibility re current mental health		x			
6/7	Age Screening	Date of birth	1 item	x			
6/7	WEMWBS	Primary outcome measure (ECoWeb- PROMOTE); secondary outcome (ECoWeB- PREVENT)	14-item	Х	X	Х	X
6/7	LIDAS current and past	Screening for past depression	Conditional questionnaire asked ever and last 3 months ranging 4	X, Last 3 months,		X, last 3 months	X, last 12 months
	inclusion exclusion		questions to 22 depending on answers	and ever			
	criteria items		3 Conditional risk questions				
			7 other items				
			On past health;				
6/7	PHQ9	Primary outcome (ECoWeB-PREVENT), secondary outcome (ECoWeB-PROMOTE)	9-item plus 3 conditional risk questions	x	x	Х	Х

			parental past health 2 items				
End of	screening and st	art of EC/risk of measures					
6/7	GAD7	Secondary outcome measure	7-item	Х	Х	Х	Х
WP4	RRS Brooding	Used for EC. Used for risk and personalisation algorithm	5 items	x	x	x	x
WP3b	Rejection	Used for EC	16 items	х	x	х	х
	sensitivity questionnaire	Used for risk and personalisation algorithm					
6/7	WSAS	General Functioning	5-item	Х	Х	Х	Х
WP4	PSWQA short	Used for EC	9 items	x	x	х	x
	form	Used for risk and personalisation algorithm					
WP5	GERT	Used for EC	20 videos	x	x	х	x
	(Geneva Emotion	Used for risk and personalisation algorithm					
	Recognition						
WP5	Task) CEUT-short	Used for EC	6 items with 4 options				
VVF3	form		o items with 4 options	X	x	x	x
		Used for risk and personalisation algorithm					
6/7	Demographics	Self-educational level,	2 questions in 6 parts	X	Status	status	status
					only	only	only
WP3b	Achievement	Used for EC	14 items in 3 versions	x	x	x	x
	Appraisal	Used for risk and personalisation algorithm					

WP3b	Achievement Emotion Questionnaire	Used for EC Used for risk and personalisation algorithm	12 items in 3 versions	x	x	x	x
6/7	EQ5-D3L	Quality of Life	6-item	Х		Х	Х
WP6	ADSUS- adapted Physical health demographic	Estimate of health costs	2-14 items 1 item	X (excludi ng anxiety and depressi items)		X 3mth	X 12mth
End of s	screening/tailoring	measures and start of additional measures					
WP 3a	EMO Dis	Control	4 items				
	control belief scale						

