The main indicators of harm will be the completion of questionnaires by the participants at all 4 assessments (baseline, 1 month, 3 month, 12 month). Questionnaires will be automatically screened for signs of severe distress (for example, defined as scores above 20 on PHQ-9 for depression or reports of suicidal ideation), with automatic programmed questions following up to ascertain aspects of risk and to automatically provide users with recommended advice and signpost towards help (family doctor, local hospital, relevant charities; e.g., website link to the Samaritans in the UK, link to Childline; to the "Teléfono de la Esperanza" in Spain; to websites providing contact details of psychotherapists and psychiatrists in Germany: http://www.bptk.de/service/therapeutensuche.html; portal site for mental wellbeing in Flanders http://www.geestelijkgezondvlaanderen.be/ and the register of clinical psychologists in Flanders http://www.vvkp.be/psycholoog/zoeken). Other indicators would be report of worsening symptoms or suicidality in direct contact from participants to the research team.

For all participants (because all participants receive an app), to further assess potential harms, we will include brief open questions to assess potential harm from the interventions (e.g. "How you have any problems with the app? Has any aspect made you feel worse?), whilst minimizing participant burden (at 3 and 12 months assessments). Potential adverse events will also be assessed using additional questions relating to hospitalisation and emergency care within the ADSUS questionnaire.

Individuals reporting severe levels of symptoms or meeting diagnostic criteria for depression will be offered guidance to seek appropriate help from their GP/family doctor, occupational health or student well-being service should this seem necessary. In addition, there will be a help option built into the app, where users can seek information on commonly occurring symptoms and difficulties and be directed to relevant contacts and links.

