9.3 Recording and reporting of SAEs, SARs AND SUSARs

All serious adverse events that are trial or treatment related will be recorded and immediately reported to the Chief Investigator and within 2 working days to the trial sponsor. If these are also classed as unexpected they will be reported to the relevant ethics committees. We will, in line with other complex intervention studies, monitor non-serious adverse events, serious adverse events that are not trial or treatment related, serious deterioration, and active withdrawals from treatment, with specific questions in the follow-up and in response to specific participant-initiated reports. Symptoms of depression or anxiety will not be defined as adverse events unless suicidal ideation, plans or an attempt has been made. The reporting period for all events and reactions will be from referral to 12month post baseline follow-up. Data on any adverse events will be collected by a member of the research team at each assessment.

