16.4 Schedule of Procedures

Table 16 The Schedule of Procedures

Procedures	Screening	Baseline (at same time as screening)	1 month Follow Up	3 month follow up	12 month follow up
Informed consent	Yes	Yes	Yes	Yes	Yes
Further Demographics	DOB Gender	Occupation Education level	Occupation DOB	Occupation DOB	Occupation DOB
Mental Health History	Yes	No	No	No	No
Current Physical conditions	No	Yes	No	Yes	Yes
Current medications	No	Yes	No	Yes	Yes
Eligibility assessment	Yes	No	No	No	No
Randomisation	No	Yes	No	No	No
Access to intervention	No	No	Yes	Yes	Yes
Compliance with intervention	N/A	N/A	No*	No	No
Assessment of wellbeing and depression	Y	N	Y	Y	Y
Assessment of emotional competence	Ν	Y	Y	Y	Y
Assessment of current functioning	N	Y	Y	Y	Y
Assessment of service use	N	Y	N	Y	Y
Adverse event assessments	N	N	Υ	Y	Y

*There are App notifications to the ppt to aid compliance and there is summary reporting of compliance, but no specific check at follow up as this would break blind

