16.5 Safety Reporting Flow Chart

Safety Flow Chart Version 1

AE reported on screener follow up. CTU website logs all AE and reported reasons

Website sends alert to site PI, site researcher and trial manager if AE reported and ppt ticks that its related to trial participation AE reported to site Researcher via email or phone, Risk log to be completed and submitted to site PI within 2 days.

AE Monitoring

All sites to produce end of monthly report of AE/SAE, unblindings and protocol violations to trial manager

Site researcher attempts to contact ppt within 2 days to find out more if insufficient data to complete risk log

Trial manager to review site reports and CTU websites log of AE/SAE at the end of every month and provide monthly report for CI and DMEC representative /

If SAE reported to site Researcher via email or phone or website alert Risk log to be completed (contacting ppt if necessary) and submitted to site PI, trial manager and CI within 2 working days.

> If SAE reported to CI TM/CI informs the sponsor, steering committee and DMEC within 2 working days of event being reported

If serious concerns for patient wellbeing/scientific rigor then discussion with ethics committee within 7 days of event being reported

SAE check-AE questions to be asked at follow up, or if reported to the site researcher by phone/email: Have you experienced any health emergencies, accidents, unplanned hospital admissions in the last 3 months? What happened? (please describe) What caused this? Please tick all that apply Sports injury Traffic accident Assault Self injury Taking part in the trial Physical illness Work Other please state

AE check-Overall, has taking part in the trial so far made you feel much worse.....no effect.....much better? Please give details Have you had any problems with the App. If yes please give details:

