## 3.8 Timing of outcome assessments

Follow-up timepoints are at 1-, 3- and 12-month follow-up (3-month follow-up is the primary timepoint). Each participant will have a scheduled follow-up date for each of the three follow-up timepoints, to be allocated on date of randomisation. Data collection will be sought within a 14-day window (within 7 days before or after the scheduled date) for 1-month follow-up. Data collection will be sought within a 28-day window (within 14 days before or after the scheduled date) for 3- and 12-month follow-up. Data collected outside this window will not be included in the primary analysis, although sensitivity analyses including all collected data will be performed.

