#### 6.10 Adverse events

The main anticipated adverse event in this trial is deliberate self-harm. Serious adverse events will be reported descriptively by treatment arm, also the number of participants in each treatment arm who have experienced at least one serious adverse event will be reported. Inferential analyses will also be performed using the count of events (Poisson or negative binomial model) and the number of participants experiencing the outcome at least once during the 12-month follow-up period (logistic regression), using observed data on an ITT principle with adjustment for covariates as for the outcome data analyses (Table A.14).

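### The dedicated serious-event question recalls only 3 months, so at the 12-month follow-up it skips months 3 to 9; AD-SUS covers hospital and emergency contacts there, but nothing scheduled prompts for self-harm without such contact

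*Protocol*

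**What the plan says.** Protocol 16.5 (Safety Reporting Flow Chart) gives one question for serious events, to be put at follow-up or when an event is reported by phone or email: "Have you experienced any health emergencies, accidents, unplanned hospital admissions in the last 3 months". A free-text description and a list of possible causes follow, and self injury is one of the causes. Only one recall period is given. Protocol 16.4 marks "Adverse event assessments" at the 1-, 3- and 12-month follow-ups.

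The period of interest is longer. Protocol 9.3 states: "The reporting period for all events and reactions will be from referral to 12month post baseline follow-up". SAP 6.10 names deliberate self-harm as the main adverse event expected. It plans models for the count of serious events and for "the number of participants experiencing the outcome at least once during the 12-month follow-up period".

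Three other passages bear on the point:

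- Protocol section 8 (Adverse Events): "Potential adverse events will also be assessed using additional questions relating to hospitalisation and emergency care within the ADSUS questionnaire". Protocol 3.3 (Health Economics Measures) and SAP 8.8 have the 12-month AD-SUS ask about services used from the 3-month assessment onward.
- Protocol 16.5 also has a general check, "Overall, has taking part in the trial so far made you feel much worse". It has no time limit, but it asks about the perceived effect of taking part, not about emergencies, admissions or injuries.
- Protocol 3.7 (Table 16) changes the recall of the depression questionnaire (LIDAS) by visit, ending with "X, last 12 months" at 12 months. Protocol 16.5 shows no such variant of the serious-event question.

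**The concern.** The follow-up visits at 3 and 12 months are nine months apart, and a 3-month recall at the second cannot bridge that interval. The SAP nevertheless treats the serious-event data as a 12-month record and compares arms on it. Table A.14 would then show 12-month counts with no sign that direct questioning covered only part of the period.

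The gap matters most for self-harm that did not lead to hospital or emergency care. The cause list attached to this question is the only scripted follow-up item that mentions self injury. The suicidality items in Protocol 16.1 ask about thoughts, intention and plans over two weeks, so they do not reach back either.

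There is a smaller problem at the other end. At 1 month, a 3-month recall extends to before the participant was randomised and overlaps the recall at the 3-month visit. SAP 6.10 counts events during follow-up, so events reported at 1 month need dates before they can be placed.

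**Working it through.** The documents give no coverage figure to reproduce. The check takes the union of the recall intervals and compares it with the follow-up period.

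**Inputs**
- Recall: 3 months (Protocol 16.5).
- Visits: 1, 3 and 12 months (Protocol 16.4).
- Windows: ±7 days at 1 month; at 3 and 12 months, "within 14 days before or after the scheduled date" (SAP 3.8). These windows govern outcome data and serve here only as a plausible range of visit dates.
- Convention assumed: 1 month = 30 days, 3 months = 91 days, 12 months = 365 days.

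**Months not asked about, all visits completed**
- Gap = 12-month visit day − 91 − 3-month visit day.
- On schedule: 365 − 91 − 91 = 183 days; 183/365 = 50%.
- Smallest: 351 − 91 − 105 = 155 days; 155/351 = 44%.
- Largest: 379 − 91 − 77 = 211 days; 211/379 = 56%.

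The denominator is the participant's actual follow-up (351 or 379 days).

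**3-month follow-up missed, 1- and 12-month completed** (Protocol 10.1 allows for 40% attrition at 3 months)
- On schedule: 365 − 91 − 30 = 244 days; 244/365 = 67%.
- Smallest: 351 − 91 − 37 = 223 days; 223/351 = 64%.
- Largest: 379 − 91 − 23 = 265 days; 265/379 = 70%.

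**Reach before randomisation at 1 month**
- 91 − 30 = 61 days (91 − 37 = 54 to 91 − 23 = 68).
- On schedule, the 1- and 3-month recalls share the 30 days after randomisation.

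**Adding AD-SUS**
- Its 3-month version covers baseline to 3 months and its 12-month version covers 3 to 12 months. For hospital and emergency contacts the gap is therefore 0 of 12 months when both are completed.
- For events without such contact, the 183-day gap remains.

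**After rewording**
- Recall since the last assessment: 30 + 61 + 274 = 365 days, so no gap.
- The 12-month recall becomes 365 − 91 = 274 days (about 9 months), or 365 − 30 = 335 days (about 11 months) if the 3-month follow-up was missed.

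**The case against.** The strongest reply is that the trial does not rely on this question alone. Protocol section 8 makes the AD-SUS hospital and emergency items a source of adverse events, and at 12 months they reach back to the 3-month assessment. The SAP is to be read with the protocol (SAP 1.4), so its silence on sources does not exclude AD-SUS. Serious events as defined in Protocol 9.1 are mostly deaths, life-threatening events, admissions or lasting disability. Deaths are notified separately (9.5), and most of the rest involve service contact. Participants may also report events themselves, and sites check at follow-up (9.3, 9.4).

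This stands, and it rules out a reading that a reader might draw from the 50% figure: that half the 12-month period has no prompt for serious events at all. The documents do not support that. What remains is narrower. Events without hospital or emergency contact are not prompted in months 3–9, and no text says how an admission reported on AD-SUS becomes an entry in the SAE data. SAP 6.1 labels AD-SUS as a health economic measure.

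A reader might also infer that duplicate or misdated early events would distort Table A.14. That is weaker than it looks. The SAE report form in Protocol 16.1 has a date field, an SAE form is part of the eCRF (Protocol 12), and an outcome of at least one event cannot be inflated by counting the same event twice. The residual concern is the event-count model, because the online item itself asks for no date.

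Finally, 16.5 is a flow chart and not the live questionnaire. Since LIDAS and AD-SUS recall vary by visit, the SAE item may vary too. A fixed 3 months is the literal reading, but it cannot be confirmed from these documents.

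**Conclusion.** The point holds in a limited form. If 16.5 is followed as written, the dedicated question misses 183 of 365 days (155 to 211 with the visit windows), rising to 244 days when the 3-month follow-up is missed. AD-SUS fills this for hospital and emergency contacts, subject to an unstated link to the SAE data. It does not fill it for self-harm or other events without such contact.

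These are days without a question, not events lost. The documents give no event rate or capture rate, so the number missed cannot be computed. A reader might infer that the arm comparison is biased; nothing shows this, because all arms receive the same question at the same visits. No efficacy result is affected. The conclusion assumes that the live form uses the wording in 16.5 at every visit.

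**What to change.** In Protocol 16.5, reword the recall to 'since you joined the trial' at 1 month and 'since your last assessment' at 3 and 12 months. At 12 months, show the 3-month follow-up date, or the last completed assessment if that is earlier. Add the date of the event to the online item.

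In SAP 6.10, name the sources of SAE data. Before each database lock, compare overnight stays and emergency attendances on AD-SUS with the adverse event log. Review unmatched ones blind to arm against the definitions in Protocol 9.1, without counting them automatically as serious.

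The cost is one changed online question, one extra field, short edits to the flow chart and SAP, and one matching step on data already collected. The price is longer recall at 12 months: about 9 months, which AD-SUS already uses when the 3-month assessment was completed, or about 11 months if the 3-month follow-up was missed. Some reviewed admissions will not qualify as serious events. The cross-check cannot find self-harm without service contact, so the rewording is the main change. If the live form already varies recall by visit, correct the text of 16.5 to match it.

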Adult Service Use Schedule (ADSUS- adapted)	The ADSUS is a well-established measure within the health economics field used to index relevant health and social care costs for trial participants. It has been used for adults and adapted for adolescents, and developed in previous trials. It asks a series of readily adaptable questions (for context) about how many times the participant has seen various	The AD-SUS has been used to support health economic analyses in a number of large-scale clinical trials (e.g., PREVENT, COBRA) (e.g., Kuyken et al., 2015; Green et al., 2011). Versions of the AD-SUS have been developed in a number of clinical trials (Byford et al., 1999; 2006; 2007).

Measure		Description	Reliability and Validity
		health professionals (e.g., GP or nurse at surgery or at home; psychiatrist, therapist), had overnight stays in hospital or hospital appointments or attendances, medication use and use of social services. This measure is used to estimate the direct healthcare and social care costs of individuals who do or don't receive an intervention.	
BACKGROUND DEMOGRAPHIC MEASURES	AND		
Demographics		Date of birth, gender, country in which live	
Educational		Educational achievement will be assessed in three standard	These are standard means for assessing
achievement		and well-established ways: (a) a hierarchical classification of the highest level of completed education as self-reported by the participant using six categories based on the International Standard Classification of Education (ISCED) 1997 (elementary/primary level; lower secondary, upper secondary; post-secondary non-tertiary; first stage of tertiary education; secondary stage of tertiary education); (b) years of completed full-time education to date; (c) self-reported grades of the main subjects (mathematics, native language, first foreign language) [where applicable].	educational attainment, and as recommended by the guidelines Report on Monitoring socio- economic inequalities in health in the European Union, prepared by the Health Monitoring Program of the European Commission.

Measure	Description	Reliability and Validity
LIDAS (Lifetime	The Lifetime Depression Assessment Self-report	Sensitivity and specificity were adequate. User-
Depression	questionnaire (LIDAS), Bot et al, 2017) assesses lifetime	friendliness of the instrument was rated high.
Assessment Self-		Median completion time was 6.2 min. Sensitivity

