Several measures in the cohort will enable us to make quantitative estimates of economic and social benefits and of change in inequality, including (a) educational attainment; (b) change in occupational status, (c) a self-report scale of functional impairment in work and social settings (see Table 1), (d) a well-established measure of quality-of-life (EQ-5D-3L). We will test whether the personalised digital EC self-help enhances these outcomes relative to online CBT self-help and usual care (including self-monitoring) controls, and whether the interventions benefit those specifically disadvantaged on these outcomes at baseline (i.e., those with social or health inequalities, e.g., migrants, low SES).

Health and social care utilisation will be collected using an adapted version of the Adult Service Use Schedule (AD-SUS). Developed for mental health trials, the AD-SUS questionnaire quantifies the use of healthcare resources, use of medication and employment and time off work over the trial including follow up (Richards et al., 2016, Kuyken et al, 2015, Byford et al., 1999; Barrett et al., 2006). Adaptation will include time away from school or college together with changes to the wording to ensure relevance across the four countries. The AD-SUS will be administered at baseline to assess use of services in previous 3-months, at 3-month follow-up, ask about use of services since the baseline interview, and 12-month follow-up, ask about use of services since the 3-month interview.

The adapted AD-SUS will enable a preliminary estimate of per person costs in each country using recommended methodology for economic evaluation (Drummond et al, 2015).

Demographic information will be collected at baseline including age, sex, country of birth, country where currently reside, ethnic group, educational level, occupation, and parent's occupation. Occupational status of participant and parent will be used as an index of socio-economic status.

Additional measures: Emotional Competencies – potential mediators of clinical outcomes

We will assess the EC abilities using the instruments developed in WP3-5 at baseline, 1 months, 3 months and 12 months, enabling us to examine whether the interventions differentially change EC skills and whether this mediates change in symptoms.

Measure	Description	Reliability and Validity
WP3a		

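### The SAE check in protocol 16.5 looks back three months, so at the 12-month visit this item does not ask about months 3 to 9

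*Protocol*

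**What the plan says.** - **The item.** Protocol 16.5 sets out an SAE check for use at follow-up, or when a participant reports something by phone or email: "Have you experienced any health emergencies, accidents, unplanned hospital admissions in the last 3 months". A free-text description and a list of causes follow; the causes include self-injury, assault and traffic accident. No other look-back is shown for any visit. A separate AE check asks whether trial participation has so far made the person feel better or worse.
- **The period to be covered.** Protocol 9.3: "The reporting period for all events and reactions will be from referral to 12month post baseline follow-up". The same section has adverse-event data collected at every assessment, and the row "Adverse event assessments" in the schedule (protocol 16.4) is marked yes at 1, 3 and 12 months.
- **The analysis.** SAP 6.10 names deliberate self-harm as the main anticipated adverse event. It models the count of serious adverse events and "the number of participants experiencing the outcome at least once during the 12-month follow-up period", reported in Table A.14.
- **Visit windows.** SAP 3.8: "Data collection will be sought within a 28-day window (within 14 days before or after the scheduled date) for 3- and 12-month follow-up". For the 1-month visit the window is 7 days either side.
- **Recall in other measures.** The AD-SUS changes with the visit: "12-month follow-up, ask about use of services since the 3-month interview" (protocol 3.3). So does the LIDAS, whose entry for the final visit is "X, last 12 months" (protocol 3.7).
- **A second source.** The adverse events section of the protocol also names AD-SUS questions on hospital and emergency care as a source of adverse events.

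**The concern.** A three-month look-back fits a visit that comes three months after the previous one. Here the last interval is nine months. The item that feeds the SAE log then asks about only the final third of that interval, while the analysis describes the full 12 months. The measures that do change their recall by visit suggest an oversight rather than a choice.

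What is at stake is completeness of the safety record for the event the SAP expects most. The SAE check is the only follow-up item shown that offers self-injury as a cause. Self-harm in months 3 to 9 that led to no service contact would reach the record only if the participant volunteered it.

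The 1-month visit raises a smaller question. A three-month look-back there reaches back before the person joined the trial, and the first month is asked about again at 3 months.

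**Working it through.** The plan gives no figure for this point, so there is none to reproduce. The check is interval arithmetic.

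**Inputs.** Visits at 1, 3 and 12 months after randomisation (protocol 7.7), taken as days 30, 91 and 365. Look-back of 3 months, taken as 91 days (protocol 16.5). Visit windows of 7 days either side at 1 month and 14 days either side at 3 and 12 months (SAP 3.8).

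**Step 1: what the item covers.** A visit at month v asks about v − 3 to v.

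| Visit | Months asked about |
|---|---|
| 1 month | −2 to 1 |
| 3 months | 0 to 3 |
| 12 months | 9 to 12 |

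After randomisation these cover 0 to 3 and 9 to 12, which is 6 of 12 months.

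**Step 2: length of the gap.** Gap = (day of 12-month visit − 91) − day of 3-month visit.

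- Nominal: (365 − 91) − 91 = 183 days.
- Shortest, 12-month visit early and 3-month visit late: (351 − 91) − 105 = 155 days.
- Longest, 12-month visit late and 3-month visit early: (379 − 91) − 77 = 211 days.

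**Step 3: missed visits, for this item alone.** Someone seen only at 12 months is asked about 3 of 12 months. Someone seen at 1 and 12 months is asked about 1 + 3 = 4 of 12, if the item is used at 1 month.

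**Step 4: the 1-month visit, if the item is used there.** Days before randomisation = 91 − visit day. At day 30 this is 61 of 91, or 67%. Across the window it runs from 91 − 37 = 54 to 91 − 23 = 68 days. Month 0 to 1 is then asked about at both the 1-month and the 3-month visit.

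**Step 5: what the other sources add in months 3 to 9.**

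- *AD-SUS:* covers months 3 to 12 for hospital and emergency use. As described in protocol 3.3 it asks "about how many times the participant has seen various" professionals, and about hospital stays and attendances; no item on cause is shown. SAP 6.10 does not say how its answers enter the SAE count.
- *PHQ-9 item 9 and its three risk questions (protocol 16.1):* asked at each follow-up, but they look back two weeks, and the risk questions concern thoughts, intention and plans.
- *AE check:* covers the trial to date, but asks about feeling better or worse, not about events.
- *Spontaneous reports:* logged, but they depend on the participant.

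**Step 6: the reworded item.** Asking from randomisation at 1 month and from the last completed assessment afterwards gives 0–1, 1–3 and 3–12. That is 12 of 12 months, without overlap and without time before randomisation.

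**The case against.** The strongest reply is that 16.5 is a flow chart and not the follow-up form, which is not in the documents. The chart may abbreviate an item that the live form already varies by visit. That stands as a limit: the point concerns the wording in 16.5, and no other wording is shown.

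A second reply is that the trial does ask about months 3 to 9. A reader might infer from the item that it does not. The documents do not support that inference, because the AD-SUS is a named adverse-event source and covers hospital and emergency care from month 3 to month 12. Its additional questions are not reproduced, so they may record more than Table 13 shows. This reply narrows the point to events without service contact.

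A third reply is that such events are rarely serious, and that the question's stem (emergencies, accidents, unplanned admissions) fits minor self-injury poorly whatever the look-back. This stands in part. A longer look-back will not capture self-injury that the participant does not see as an emergency or accident. But the protocol's adapted list of relevant events (9.1) includes self-harm and suicide attempts, and its SAE report form places them under life-threatening events, separately from hospitalisation. Such events are therefore in scope without an admission.

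A fourth reply concerns the 1-month visit. Protocol 9.3 and 16.4 place adverse-event assessment there but do not say which items are used; the open harm questions are placed at 3 and 12 months only. A reader might infer that events from before randomisation, or counted twice, would enter Table A.14 and dilute a difference between arms. That would need this exact item at 1 month, no other source, and no exclusion by date. The SAE report form already has a date field, and SAP 6.10 ties the participant-level analysis to the 12-month follow-up period, where a repeated report changes nothing. No estimate of dilution is justified.

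**Conclusion.** The point holds for the item as worded in protocol 16.5. At the 12-month visit it does not ask about months 3 to 9, a stretch of 183 days nominally and 155 to 211 days within the SAP windows, although the reporting and analysis period runs to 12 months. The loss falls mainly on self-harm, assaults and accidents in that stretch that led to no service contact, and on the cause of events that the AD-SUS records only as contacts.

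A reader might go further and infer bias between arms. The documents do not support that: the items are the same in all three arms, so the expected effect is under-ascertainment throughout.

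The 1-month part is conditional. If the same wording is used there, as 9.3 and 16.4 suggest, about two-thirds of the look-back precedes randomisation and the first month is asked about twice.

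The conclusion assumes that the live form follows 16.5. It is a modest point, worth correcting because the remedy is cheap.

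**What to change.** 1. In protocol 16.5, word the look-back as *since you joined the trial* at 1 month and *since your last completed assessment* at 3 and 12 months. Show the date of that assessment, or of randomisation if there was none, so that a missed visit leaves no gap.
2. Carry the date field of the existing SAE report form into the item, so that each event is dated.
3. In SAP 6.10, state that only events after randomisation count, each once.

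The cost is one reworded item in four languages, a date field and a sentence in the SAP. Recall at the 12-month visit becomes nine months, as the AD-SUS already requires, or up to 12 months if earlier visits were missed, and some minor events will be forgotten. Visits at 1 and 3 months already completed keep the old wording, so recall is mixed at those visits. It need not be mixed at 12 months. The amendment history has the recruitment website going to the ethics committee on 3 August 2020; if recruitment began no earlier, the first 12-month window opens on 20 July 2021 (3 August 2021 less 14 days), after the protocol date of 5 July 2021. If the live form already varies the recall, only 16.5 and the SAP sentence need correcting.
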